**Effect of in vitro fertilisation (IVF) hormonal
therapy on metabolic, endocrine and
inflammatory status in IVF-conceived
pregnancy**

NCT03426228

Chapter 1: Aim of the study and Objectives

1. To explore the short-term effects of IVF hormonal therapy on maternal metabolic and inflammatory status, including:
 - i. Risk of glucose intolerance and insulin resistance
 - ii. Risk of other metabolic, endocrine and inflammatory disturbances (including lipid profile, gut microflora and thyroid function)
2. To identify possible early predictors of GDM and other metabolic-related adverse outcomes in IVF-conceived pregnancies.

Chapter 2: General Methods

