2.6. Study Protocol

After an overnight fast of 8 hours, there was collection of 10 ml of blood at four pre-defined time points during the IVF protocol:

1. **Phase 1** – At baseline, egg maturation (starting IVF therapy)
2. **Phase 2** – Week 2 – Egg retrieval (OPU procedure)
3. **Phase 3** – Week 4 – At pregnancy test (β -HCG test)
4. **Phase 4** – Week 12 (one week after completing IVF hormonal therapy for pregnant group).

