2.7. Blood Tests

A trained nurse was in charge of measuring anthropometrics and clinical parameters (e.g. weight and blood pressure), in addition to taking fasting blood samples. The socio-demographics, medical and pregnancy histories of each patient

were recorded in their file. Blood tests were conducted at in the phlebotomy room and transferred to the lab (in-house) for analysis. Tests results were available on the clinics internal server at the end of each day.

Table 1: List of Blood Tests at Each Stage of the Study

Type of Tests	Phase 1- Baseline (Start IVF treatment)	Phase 2- Week 2 (Egg retrieval)	Phase 3- Week 4 (β - HCG test)	Phase 4- Week 12 (Final)
Female reproductive hormones: FSH, LH, oestrogen, progesterone	✓	✓	✓	
HbA1c	✓			✓
Fasting glucose	✓	✓	✓	✓
Fasting insulin	✓	✓	✓	✓
TSH	✓			✓
Fasting lipid profile	✓			✓
Adiponectin	✓			✓
LBP	✓			✓
β -HCG pregnancy	✓		✓	
Body weight	✓			✓

*Green highlight represents stage where non-pregnant vs. pregnant women groups were distinguished; FSH: follicle-stimulating hormones; LH: luteinizing hormone; HbA1c: glycated haemoglobin A1c; TSH: thyroid-stimulating hormone; LBP: lipopolysaccharide binding protein; β -HCG: beta-human chorionic gonadotrophin

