Appendix 1. Anthropometrics and Medical History Questionnaire

Effects of fertility drugs on glucose homeostasis, and other metabolic parameters on patients undergoing In Vitro Fertilisation (IVF) [NCT03426228](#)

Subject Name:

Telephone No:

E-mail:

Age	
Height	
Weight	
BMI	
Nationality	
Smoking	
Parity	

Past Illness and Surgeries

Drug History

Family History

Women Health

Cycle:	Regular	Irregular
--------	---------	-----------

History of GDM:
Previous IVF trials:

Blood Analysis

Type	Level/ Unit	Frequency
Fasting glucose		4 times
Serum insulin		4 times
Lipid profile		Twice
FSH, LH		4 times
Oestrogen, Progesterone		4 times
Beta-HCG		Once

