**Effect of in vitro fertilisation (IVF) hormonal therapy
on metabolic, endocrine and inflammatory status in
IVF-conceived pregnancy**

NCT03426228

Statistical Analysis

1. Effects of IVF Therapy

Data analysis was performed with the Statistical Package for the Social Sciences (SPSS) software version 21.0 for Windows (SPSS, Chicago, IL). Parameters normality was confirmed with the Shapiro-Wilk test. Non-parametric Wilcoxon test for two related samples was conducted to assess changes at baseline vs. post-IVF treatment (12 weeks) within groups (pregnant or non-pregnant). Non-parametric Mann-Whitney U test for two independent samples was used to compare the two groups pregnant vs. non-pregnant, at baseline and at 12 weeks. Bivariate correlation was used to determine correlations between the different anthropometric and metabolic parameters at week 12. Data from the two groups were analysed separately. Linear regression was used for assessment of association of change in glucose level at 12 weeks (dependent variable) with change in other anthropometric and biochemical parameters, separately for each group. Changes in glucose and insulin levels (and the resulting HOMA-IR) throughout IVF therapy (baseline, 2, 4 and 12 weeks) were determined with the mixed model for repeated measures test. Significance level was set at $p < 0.05$ and 95% confidence interval.

2. Anthropometrics and Biomarkers of Gestational Diabetes Mellitus (GDM)

In the pregnant group, the Mann-Whitney U test for two independent samples was used to compare data at baseline with 12 weeks, for comparison between women who later developed GDM to the non-GDM group. Changes at baseline, 4 and at 12 weeks were assessed by non-parametric Wilcoxon test (two related samples) within groups (future GDM or non-future GDM women). Predictors of GDM were assessed using binary logistic regression, adjusting for the following variables: age and history of PCOS.

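### Does the SAP fall short by analysing predictors of GDM only, and by not saying how GDM status was obtained?

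*SAP*

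**What the plan says.** Objective 2 in Protocol Chapter 1 seeks "early predictors of GDM and other metabolic-related adverse outcomes in IVF-conceived pregnancies" and does not list the other outcomes.

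SAP section 2 is the only place where predictors of a pregnancy outcome are analysed. It has three parts, all built on GDM: a Mann-Whitney test "for comparison between women who later developed GDM to the non-GDM group", Wilcoxon tests "within groups (future GDM or non-future GDM women"), and a regression adjusted for age and PCOS history ("Predictors of GDM were assessed using binary logistic regression").

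On data collection, Protocol 2.6 schedules blood at "four pre-defined time points during the IVF protocol", the last at week 12. Protocol 2.7 ("Table 1: List of Blood Tests at Each Stage of the Study") and Appendix 2 also stop there. The one GDM item on a form is "History of GDM" in Appendix 1, a background characteristic. Protocol 2.3 adds that the clinics provide obstetric care on site and follow most women through to delivery.

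**The concern.** Two things look wrong. First, the objective covers more than the analysis. If nothing beyond GDM is analysed, part of objective 2 goes unanswered. If further outcomes were picked once the data were in, a reader could not tell planned findings from selected ones.

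Second, GDM status defines the groups in every section 2 analysis, yet it appears to arise after the last study visit, and no source, criterion or window is given. With three clinics, a reader may ask whether one criterion applied throughout, and what happened to women not followed to delivery. If their status was handled badly, the predictor odds ratios could be distorted.

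**Working it through.** The plan states no sample size, GDM rate or power figure, so there is none of its own to reproduce. The check is mainly a comparison of texts, with some arithmetic on assumed inputs.

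**1. Scope.** Objective 2 names two outcome types; SAP section 2 analyses one. SAP section 1 does not supply the other. Its regression concerns "association of change in glucose level at 12 weeks (dependent variable) with change in other anthropometric and biochemical parameters". Six rows of Protocol Table 1 that could enter it (HbA1c, TSH, lipids, adiponectin, LBP, weight) are measured only at baseline and week 12, so their changes span the same interval as the glucose change. The model is also fitted in the non-pregnant group. It belongs to objective 1. The documents do name and test other metabolic measures, but as effects of therapy, not as outcomes to be predicted. The scope gap is therefore confirmed, in that narrow sense.

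**2. Does the scope gap inflate error?** Eight Table 1 rows measured at baseline are candidate predictors: HbA1c, glucose, insulin, TSH, lipids, adiponectin, LBP and weight. With independent tests at 0.05, the chance of at least one false positive is

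- one outcome: 1 − 0.95^8 = 0.337
- three outcomes: 1 − 0.95^24 = 0.708

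The first figure comes from the number of predictors. It applies equally to GDM alone, so narrowing objective 2 would not reduce it. The second needs extra outcomes to have been chosen later. Nothing in the documents supports that: the SAP is written in the past tense and mentions GDM only. If no other outcome was analysed, there is no added inflation.

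**3. Does unknown GDM status bias the odds ratio?** A logistic regression can use only women with a recorded outcome, so treating unknowns as missing is what the model does by default. Assume GDM risks of 0.30 and 0.15 at two predictor levels:

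- full data: (0.30/0.70) / (0.15/0.85) = 0.4286 / 0.1765 = 2.43
- 5% of cases and 30% of non-cases lost at **both** levels: each odds is multiplied by 0.95/0.70, which cancels, leaving 2.43
- the same loss at the higher-risk level only: 2.43 × 0.95/0.70 = 3.30
- 30% of cases and 5% of non-cases lost at the higher-risk level only: 2.43 × 0.70/0.95 = 1.79

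Bias in the odds ratio therefore requires the ratio of case to non-case retention to differ between predictor levels. Loss related to GDM is not enough by itself.

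**4. Precision.** If the same share is lost everywhere, the standard error grows by 1/√0.95 = 1.026 at 5% loss and 1/√0.70 = 1.195 at 30%. Those shares are assumptions, and writing down a missing-data rule would not recover the information.

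**The case for a change.** The best case for acting is that GDM status underlies everything in SAP section 2 and cannot be reproduced from the documents. Follow-up of most women is a remark about the clinics, not an ascertainment rule. A woman lost after week 12 could have been placed in the non-GDM group rather than set aside. A few sentences would settle it, at no clinical cost.

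Part of this stands. The source, criterion and window are absent, no redaction explains their absence, and the SAP does not say how women of unknown status were handled. The report of the study would ordinarily give these details. But the absence of a sentence is not evidence that women were misclassified, and the natural reading of non-GDM is a woman known not to have developed it. Asking for the detail improves the description without changing a test, a model or an estimate.

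On the unanswered half of objective 2, the rebuttal is weaker still. The documents describe finished work in an exploratory cohort recruited by convenience sampling, with an aim phrased in terms of possible predictors. Rewriting the objective now to match the analysis would be less open than leaving it and letting the results show that only GDM was addressed.

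**Conclusion.** No change to the plan follows. The facts behind the concern are correct: one of the two outcome types in objective 2 has a predictor analysis, and the documents state no source, criterion or window for GDM. Their consequences are small. Trimming the objective changes no result. The GDM details are ones that analysts working from clinic records would have to settle in order to form the groups at all. Leaving out women of unknown status is already the model's default.

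The size of any bias cannot be determined. The shift from 2.43 to 1.79 or 3.30 rests on assumed risks and on outcome-related loss confined to one predictor level, a pattern the documents neither show nor suggest. The conclusion assumes that no other adverse outcome was analysed as if planned, and that women without a documented status were treated as missing and not counted as non-GDM. Evidence against either assumption would reopen the point.

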2.5. Sampling Technique

The non-probability convenience sampling method was used to recruit participants for the study. Patients who were to start a fresh IVF treatment at any of the IVF Clinic branches and meeting the inclusion criteria were eligible to participate.

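### The GDM analysis can nominate associated markers, but does not plan to measure or validate how well any of them predicts GDM beyond age and PCOS

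*SAP*

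**What the plan says.** The second objective in Protocol Chapter 1 is "To identify possible early predictors of GDM and other metabolic-related adverse outcomes in IVF-conceived pregnancies". SAP section 2 gives one sentence to the assessment of predictors: "Predictors of GDM were assessed using binary logistic regression, adjusting for the following variables: age and history of PCOS".

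Two further analyses stand in the same section. One is a Mann-Whitney test within the pregnant group, "for comparison between women who later developed GDM to the non-GDM group". The other looks at change over time separately in women with and without later GDM: "Changes at baseline, 4 and at 12 weeks were assessed by non-parametric Wilcoxon test (two related samples) within groups". Neither adjusts for age or PCOS.

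The only significance rule is at the end of SAP section 1: "Significance level was set at $p < 0.05$ and 95% confidence interval". I take it to cover section 2 as well, since no other level is given there.

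Neither document mentions an AUC or ROC curve, sensitivity or specificity, calibration, gain over age and PCOS, bootstrap, cross-validation or shrinkage. Nor do they give a list of candidate markers, a selection rule, a sample size or a number of GDM cases. The sample is a convenience sample (Protocol 2.5).

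**The concern.** A significant adjusted coefficient says that a marker is associated with later GDM. It does not say how well the marker separates women who will develop GDM from those who will not, or whether it improves on age and PCOS, which cost nothing to collect. A reader of a section on predictors will want to know exactly that.

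Two things could make the results look better than they are. GDM cases are a subset of the pregnant group only; if they are few, logistic regression by maximum likelihood pushes odds ratios away from 1. And if several markers are screened or combined, the fit in the same women is better than it would be in new ones. The plan has no step that would reveal either effect.

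**Working it through.** **Inputs.** From the documents: the model and its two adjusters (SAP section 2), the 0.05 level (SAP section 1), and the measurements in Protocol 2.7, "Table 1: List of Blood Tests at Each Stage of the Study". That table yields at least 12 baseline candidates: FSH, LH, oestrogen, progesterone, HbA1c, glucose, insulin, TSH, the lipid profile counted once, adiponectin, LBP and weight. That all were candidates is an assumption. The number of women, GDM rate, marker effects and two-sided testing are also assumptions. The plan states no power, odds ratio or AUC, so there is no figure of its own to reproduce.

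**1. Association against discrimination.** For a normally distributed marker with equal SD in both groups, AUC = Φ(ln OR / √2), with OR per SD. For OR 1.8: ln 1.8 = 0.588; 0.588 / 1.414 = 0.416; Φ(0.416) = 0.66. Odds ratios of 1.5, 2, 3 and 5 give AUCs of 0.61, 0.69, 0.78 and 0.87. Sensitivity at a 10% false-positive rate, 1 − Φ(1.282 − ln OR), is then 19%, 28%, 43% and 63%.

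**2. What p < 0.05 guarantees.** With N women and a proportion p with GDM, the smallest odds ratio per SD that reaches significance is about exp(1.96 / √(N p (1 − p))).
- N = 50, 10 cases: exp(1.96 / √8) = 2.00, AUC 0.69.
- N = 100, 20 cases: exp(1.96 / √16) = 1.63, AUC 0.64.
- N = 300, 60 cases: exp(1.96 / √48) = 1.33, AUC 0.58.

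**3. Small-sample bias for one marker adjusted for age and PCOS.** Simulation, 1,500 runs per size, true log odds ratio 0.588 (OR 1.8). The last column comes from separate runs.

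| GDM cases (about) | Mean log OR, maximum likelihood | Overstatement | Mean log OR, Firth | OR when significant, maximum likelihood | OR when significant, Firth |
|---|---|---|---|---|---|
| 12 | 0.680 | 16% | 0.598 | exp(1.072) = 2.9 | 2.6–2.7 |
| 20 | 0.644 | 10% | 0.592 | exp(0.844) = 2.3 | 2.2 |
| 30 | 0.618 | 5% | 0.585 | exp(0.713) = 2.0 | 2.0 |

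Repeat simulations gave overstatements of 13–16%, 9–12% and 5–7%. Firth's method removes most of the average bias, but barely changes odds ratios that are picked out because they are significant.

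**4. Optimism.** If 12 null markers, age and PCOS (also null) all entered one model, the true AUC would be 0.50. The apparent AUC averaged 0.85 (60 women, 12 cases), 0.78 (80, 20), 0.73 (120, 30) and 0.67 (200, 50); a repeat gave 0.84, 0.78, 0.72 and 0.67. Even one null marker with null age and PCOS showed 0.65 with 12 cases, so an uncorrected AUC would mislead too.

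**5. Number of markers tested.** For 12 independent null markers, the chance of at least one p < 0.05 is 1 − 0.95^12 = 46%; for 8 it is 34% and for 24 it is 71%. Simulation with 12 markers gave 44–47%. Correlated markers would lower these figures.

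**The case against.** The objective asks only for possible predictors. It asks for no prediction model, cut-off or accuracy study, and an adjusted association between an early marker and later GDM is a legitimate way to nominate one. This stands. A reader might infer that the plan cannot show that any marker predicts GDM; the documents do not support that.

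A reader might also infer that the plan rests on adjusted odds ratios alone. It does not. Mann-Whitney and Wilcoxon tests are planned as well, and the Mann-Whitney U divided by the product of the two group sizes is the unadjusted AUC. The SAP does not even name odds ratios; they are simply the usual output of the model. But the plan uses U only as a test, and it cannot show a gain over age and PCOS.

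Third, the largest optimism figures belong to a joint model that the SAP does not describe. Each marker adjusted for two covariates is the plainer reading. And since no AUC is planned, an inflated one would not be reported. Both points are fair: the joint model is a scenario that the text leaves open.

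Finally, nothing in the documents shows that GDM cases were few, and the single-marker bias falls to about 5% by 30 cases. That also stands.

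**Conclusion.** The concern holds in a limited form. The planned tests can identify markers associated with later GDM. They cannot quantify or validate predictive value, alone or beyond age and PCOS.

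The gap between association and discrimination does not depend on knowing the sample size: under the binormal model an odds ratio of 1.8 per SD means an AUC of about 0.66. The rest is conditional. A 5–16% overstatement of a single-marker log odds ratio assumes about 12 to 30 cases and a true odds ratio of 1.8. An apparent AUC of 0.72–0.85 assumes the same range of cases and an unstated joint model. The 46% chance of a false lead assumes 12 independent null markers, each tested at 0.05.

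This does not invalidate the GDM analysis. It limits what may be concluded from it, and the remedy is cheap enough that it should be made.

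**What to change.** In SAP section 2:

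1. Name each candidate marker and its time point from Protocol Table 1. Add the markers one at a time to the model with age and PCOS.
2. For each, report the likelihood-ratio test, the AUC with and without the marker, and the difference with a 95% CI. Correct for optimism by a bootstrap that repeats any selection step.
3. State the number of GDM cases and of markers tested.
4. Describe significant markers as exploratory associations. Make claims of predictive value only with reference to the corrected AUC gain.
5. If cases are few, add Firth's penalised likelihood as a sensitivity analysis, noting that it does not remove inflation from selecting on significance.

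I would not require the CI of the corrected gain to lie above zero before a marker may be called a predictor. In one small simulation (true OR 1.8, assumed modest age and PCOS effects, 150 runs per size, not repeated), the likelihood-ratio test detected the marker in 46%, 61%, 77% and 95% of runs with 12, 20, 30 and 50 cases. Such a rule passed only 29–37%, 33–45%, 38–57% and 57–79%, depending on how the CI was built.

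The cost is SAP wording, a short script outside SPSS, and less favourable-looking results. Intervals will also be wide: by the Hanley-McNeil formula an AUC of 0.70 has a 95% CI of 0.56–0.84 with 20 cases in 100 women. No new data are needed.
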